**Single cell RNA-sequencing in blood before and after treatment.**

We propose to examine our blood samples collected before and after treatment with Pembrolizumab by single cell sequencing experiments at the Cancer Genomics Shared Resource and data analyzed by the Bioinformatics Shared Resources to determine the complex response in the immune cell populations. PBMCs from selected patients are thawed, assessed for > 70% viability, and then processed for single cell gene expression using the Next GEM Single Cell 3' GEM, Library & Gel Bead Kit v3.1 and 10X Genomics Chromium platform. Barcoded UMI-tagged libraries are sequenced on an Illumina NovaSeq 6000 targeting 4000 cells per sample at a median read depth of 50,000 reads per cell. Raw bcl and fastq data will be demultiplexed, normalized and post-processed using Cell Ranger mkfastq pipelines and QC algorithms (10X Genomics). The Cell Ranger mkfastq pipelines (10X Genomics) is used to process, QC and align sequencing reads and to optimize cell calling. Graph-based or K-means clustering algorithms implemented in Cell Ranger are applied to delineate populations of diverse immune cell lineages whose identities are frequently confirmed by the presence or absence of marker gene combinations informed by antibody-based cell sorting and identification methods, or published transcriptional signatures of FACS-sorted immune cells (42-44).

**scRNASeq data processing.** Transcript read counts will be normalized and statistically compared for differential expression between patients using DESeq2 [2] that applies the negative binomial model with independent dispersions. Differentially expressed genes (DEGs; FDR-corrected,  $p < 0.05$ ) will be analyzed by Ingenuity Pathway Analysis (IPA, [www.ingenuity.com](http://www.ingenuity.com)) and Gene Set Enrichment Analysis (GSEA) [3] to identify gene enrichment for biological processes or signaling pathways that underlie response.

Red Blood Cells (RBCs) that are left over after the isolation of plasma for metabolomics and miRNA measurement, and of PBMCs for the scRNA sequencing, instead of being discarded as per routine protocols, will be saved and utilized for testing the optimization of protocols designed to quench redox metabolism. Redox metabolism is tightly associated with all aspects of cancer pathophysiology, including response to immunotherapy and radiotherapy. However, redox metabolism remains inadequately studied and utilized in clinic due to the lack of appropriate biospecimen preservation technologies. RBC, a valuable source of redox components, will be washed and either used immediately for testing of redox preservation media or stored for future use.

Currently, simple banking of whole blood or its components fails to capture an accurate redox status of blood or tissues because of artifacts introduced by handling and the absence of redox preservation mechanism.

The research-dedicated blood samples are de-identified by the clinical study team such that a study research ID replaces any subject identifier (MRN, name). The clinical study team securely maintains the key for study IDs and patient information.

Remaining samples will be retained for future research after the study report has been finalized if agreed by patients in the ICF. Otherwise, it will be disposed.

Quad-Shot Radiotherapy in Combination with Immune Checkpoint Inhibition for Advanced/Recurrent Head and Neck Cancer  
Wake Forest Baptist Comprehensive Cancer Center  
WFBCCC60320

Oral microbiota profiling will be performed using 16S rRNA gene sequencing to characterize the bacterial diversity and composition in the saliva collected from these patients at indicated time points before and during treatment.

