### **2.3 Exploratory Objectives**

- 2.3.1 Evaluate the effect of quad- shot administration on increasing the immune activation by treatment with pembrolizumab and investigate possible mechanisms.

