### **5.3 Exploratory Objectives**

Blood will be utilized to measure the effect of immunotherapy alone as well as in combination with quad-shot therapy on increase of the circulating immune microRNA.

In addition, blood and saliva specimens will be utilized for mechanistic investigations of the effects of quad-shot on the response to immune checkpoint inhibitors. Detailed and comprehensive single cell RNA sequencing and multi-omics analysis of both plasma and exosomes fractions will be performed.

Saliva will be utilized for metabolomics and miRNA and RNAseq analysis of oral microbiome

Quad-Shot Radiotherapy in Combination with Immune Checkpoint Inhibition for Advanced/Recurrent Head and Neck Cancer  
 Wake Forest Baptist Comprehensive Cancer Center  
 WFBCCC60320

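### The single-cell analysis states only a between-patient comparison, which cannot estimate the within-patient change under quad-shot that the exploratory objective asks about

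*Combined protocol and SAP*

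**What the plan says.** Objective 2.3.1 (Section 2.3) reads: "Evaluate the effect of quad- shot administration on increasing the immune activation by treatment with pembrolizumab and investigate possible mechanisms".

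Section 5.3 gives the purpose of the specimens: "blood and saliva specimens will be utilized for mechanistic investigations of the effects of quad-shot on the response to immune checkpoint inhibitors". The sentence that follows names single-cell RNA sequencing among the methods. For circulating microRNA, Section 5.3 goes further and names a contrast, namely to "measure the effect of immunotherapy alone as well as in combination with quad-shot therapy on increase of the circulating immune microRNA".

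Section 9.1 describes the sequencing material as "blood samples collected before and after treatment with Pembrolizumab". It limits the material to some patients ("PBMCs from selected patients are thawed") and gives neither their number nor the rule for selecting them. The only statistical comparison is in the data-processing paragraph: normalised counts are "statistically compared for differential expression between patients using DESeq2", with an FDR-corrected threshold of 0.05. The resulting genes go into pathway analyses aimed at what lies behind response.

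Section 4.2 has blood drawn before each of the first five immunotherapy doses and before quad-shot. It also makes the study single-arm. Section 4.3.3 has every patient receive one quad-shot cycle. Section 11 covers the analysis of the primary and secondary objectives only, so it adds nothing on this point.

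**The concern.** The sampling schedule makes each patient their own control, but the stated test sets patients against each other. It contains no patient term, pairing, before/after contrast or unit of aggregation, and the anchor for before and after is pembrolizumab, not quad-shot.

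Two things are at stake. First, the gene list may be presented as evidence on the quad-shot mechanism although the comparison behind it does not contain that effect. Second, if several samples per patient enter the model without a patient term, the p-values behind the FDR threshold are wrong, and the error carries into the pathway analysis.

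**Working it through.** **The plan's own figure.** Section 9.1 states none for this analysis. The only precision figure, in Section 11.3, is the maximum 95% Clopper-Pearson width of 0.52 for 15 patients. It reproduces (7/15: 0.213 to 0.734, width 0.52) but concerns the primary outcome.

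**Which comparison contains the quad-shot effect.** For one gene in one cell type, write expression in patient i at time t as

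y(i,t) = a(i) + g(t) + q·Q(i,t) + error,

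where a(i) is the patient's own level, g(t) is change with time and cumulative immunotherapy, and Q is 1 after quad-shot and 0 before.

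- Between patients i and j at the same time, both after quad-shot: y(i,t) − y(j,t) = a(i) − a(j) + error. The term q cancels.
- Within a patient, after minus before: q + [g(after) − g(before)] + error. The term a(i) cancels. The term q is present, but mixed with the change in g.

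So the stated comparison omits q. The within-patient comparison contains it, but without a control arm it does not isolate it.

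**Can an earlier interval remove g?** Only in part. Section 4.2 puts quad-shot in the last week of a three-week cycle, so the interval from the pre-quad-shot draw to the next pre-dose draw is about a week or less. An immunotherapy-only interval between pre-dose draws is three weeks. The two differ in length, in time since infusion and in cumulative dosing.

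**Consequence if serial samples are treated as independent.** The plan does not say that they will be, so this is conditional. Inputs:

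- 15 patients (Section 11.3), with an assumed split of 5 responders and 10 non-responders.
- k samples per patient: 2 as a minimal before/after pair, 7 from the blood-volume table in Section 9.1. (The draws described in Section 4.2 for a patient with one quad-shot cycle add up to 5 + 1 = 6.)
- Within-patient correlation ρ assumed at 0.3, 0.5 and 0.7; the documents give no value.
- One gene, Gaussian scale, raw two-sided 5% test.

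The true variance of the group difference is larger than the test assumes by the factor 1 + (k − 1)ρ.

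| k | ρ | Factor | Simulated type I error |
|---|---|---|---|
| 2 | 0.3 | 1.3 | 0.089 |
| 2 | 0.5 | 1.5 | 0.116 |
| 2 | 0.7 | 1.7 | 0.145 |
| 7 | 0.3 | 2.8 | 0.243 |
| 7 | 0.5 | 4.0 | 0.337 |
| 7 | 0.7 | 5.2 | 0.406 |

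The normal approximation 2[1 − Φ(1.96/√factor)] agrees closely: 0.086 for a factor of 1.3, and 0.327 for 4.0. With one averaged value per patient, the simulated error returns to about 0.05 in every row.

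**The opposite error.** If before and after samples from 15 patients were compared by an unpaired test, the test would be conservative: true size 0.020, 0.008 and 0.001 at ρ = 0.3, 0.5 and 0.7. The direction of the error therefore depends on an analysis choice that the plan leaves open.

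**The case against.** The strongest reply is that a between-patient comparison suits part of what the plan wants. The objective extends to mechanisms, the pathway step in Section 9.1 is aimed at what underlies response, and the contrast of immunotherapy alone against the combination is written for microRNA, not for sequencing. On this reading the sequencing is a responder versus non-responder study and between-patient variance is the proper error. Much of this stands, and the between-patient comparison should be kept. However, Section 9.1 does not define the groups, its heading and opening sentence announce a before/after study, and Section 5.3 ties the sequencing to the effects of quad-shot. The before/after part is left without an analysis.

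It can also be said that quad-shot exposure does vary between patients: Section 4.2 allows two slots for the first cycle, and later cycles are discretionary. No such contrast is named, and the choice of slot or number of cycles is not randomised.

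A reader might infer more than the documents support:

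- *That pairing would cut the variance by 30%, 50% or 70%.* This follows from 2s²(1 − ρ) against 2s² at ρ = 0.3, 0.5 and 0.7. The comparator is an unpaired before/after test, which the plan does not contain, and the correlations are assumed.
- *That between-patient variation will swamp any treatment change, or that the gene list will be full of false positives.* Inflation arises only if serial samples are pooled as independent, which the plan does not state.
- *That a before/after quad-shot contrast would isolate the quad-shot effect.* It would not, for the reasons of timing and cumulative dosing shown above.
- *That the change needs no further sequencing.* Section 9.1 does not say which draws are sequenced.

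**Conclusion.** The concern holds in this form: the only comparison stated for the single-cell data is between patients, and in a single-arm trial where all patients receive quad-shot it cannot estimate the within-patient change that Sections 2.3 and 5.3 ask about. This follows from the design and rests on no assumed number.

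The numerical consequence is conditional. The type I error of roughly 9% to 41% applies only if repeated samples are pooled as independent, and it rests on the assumed 5/10 split and correlations of 0.3 to 0.7. Any gain in precision from a paired analysis depends on the same unknown correlation. DESeq2 itself is not at fault, since its design can carry a patient term.

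The importance is low. This is one exploratory assay in a pilot without formal hypothesis tests, and no primary or secondary outcome depends on it.

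**What to change.** In Section 9.1:

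1. Sum counts per patient, sample and cell type (pseudobulk). For the before/after comparison fit DESeq2 with design patient + time point, keeping the FDR threshold.
2. Before sequencing starts, name the time points to be sequenced and the rule for selecting patients. Define time points relative to each patient's own quad-shot date: with two permitted slots, the draw before cycle 3 falls after quad-shot for some patients and before it for others.
3. If draws on both sides of quad-shot are among those sequenced, make that the named contrast, with an earlier immunotherapy-only change as a descriptive reference. State that the contrast remains confounded with time, time since infusion and cumulative immunotherapy.
4. Keep the between-patient comparison as a separate, labelled responder versus non-responder analysis, with the groups defined and one sample, or one change, per patient.

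The cost is a paragraph of text and some added analysis work in the same software. Added sequencing is needed only if the draws around quad-shot were not already to be sequenced. The blood collection schedule does not change.

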### 11.3 Power and Sample Size

Since this is a pilot study there will be no formal hypothesis tests performed. With a sample size of 15 evaluable patients (patients must be evaluable for objective response as described in Section 7.1.1), the maximum width of a 95% Clopper Pearson exact confidence interval is 0.52 (since the interval may not be symmetric this corresponds to approximately +/- 0.26 (if the response rate is as high as 7/15). If the response rate is lower than this then the width of the confidence interval will be less. With this sample size we will be able to determine whether the response rate in this treatment is high enough to warrant future examination. Based on preliminary data presented in Table 1 the response rates from previous studies is between 13 and 36% thus we would anticipate that the response rate in this study will need to be at least this high to warrant future studies.

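### Section 9.1 sends only the FDR-significant genes to GSEA, which removes its reference genes and can hide pathways linked to response, above all when the shifts are modest and coordinated

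*Combined protocol and SAP*

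**What the plan says.** The data-processing paragraph for single-cell RNA sequencing in Section 9.1 describes a chain of three steps.

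1. Normalised counts are "statistically compared for differential expression between patients using DESeq2 [2".
2. A filter follows: "Differentially expressed genes (DEGs; FDR-corrected" at p < 0.05.
3. The genes that pass are the subject of the next verb. They "will be analyzed by Ingenuity Pathway Analysis" "and Gene Set Enrichment Analysis (GSEA) [3] to identify gene enrichment for biological processes or signaling pathways that underlie response".

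One list therefore feeds both tools. Nowhere do the documents say that GSEA receives the full ranking. They also do not state the ranking statistic, the permutation unit, the reference set for IPA, or which groups or time points are contrasted.

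The analysis serves Section 2.3, whose aim concerns "increasing the immune activation by treatment with pembrolizumab and investigate possible mechanisms". Section 11.3 plans on 15 evaluable patients and no formal hypothesis tests. Section 9.1 adds that "PBMCs from selected patients are thawed", without giving their number.

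**The concern.** IPA-type over-representation asks whether a short list contains more members of a pathway than chance would put there, so it starts from a filtered list. GSEA asks whether the members of a pathway sit towards one end of a ranking of every gene tested. The genes that show nothing are its yardstick.

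If the list is cut at the FDR threshold first, the yardstick becomes the other DEGs. The test then asks whether set members rank differently from genes that are already significant. That is not the stated purpose, which is to find pathways that underlie response. Two failures become possible:

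- A pathway full of DEGs can look ordinary because all its comparators are DEGs too.
- A pathway in which many genes each move a little may contribute few or no genes to the list, although this is the pattern GSEA is designed to detect.

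At stake is a named tool of the exploratory mechanistic work. The response-rate estimate and the secondary outcomes do not depend on it.

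**Working it through.** The plan gives no power or error rate for this step, so there is no figure of its own to reproduce.

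**Inputs from the documents.** At most 15 evaluable patients (Section 11.3); FDR cut-off 0.05 (Section 9.1); earlier response rates of 13% to 36% (Section 11.3). If responders were compared with non-responders, those rates give 0.13 × 15 = 1.95 to 0.36 × 15 = 5.4, or about 2 to 5 responders.

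**Assumptions.** 5,000 genes; a 50-gene pathway; 5 against 10 or 7 against 8 patients; normal, independent log-expression; a t-test standing in for DESeq2; 500 other genes truly shifted by 2 SD in most scenarios.

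**Formulas.** Under Benjamini-Hochberg, a single gene passes alone only if p ≤ 0.05/5,000 = 0.00001. GSEA walks down the ranking. At a set member the sum rises by |t| divided by the total |t| of the set. At any other gene it falls by 1/(N − k), where N is the list length and k the number of set members in it. On the full list the falls come from 5,000 − 50 = 4,950 genes. On the filtered list they come only from DEGs outside the set.

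**Results.** 100 runs per scenario, 300 gene-label permutations on both lists, so that only the filtering differs. Paired entries are the 5:10 and 7:8 splits.

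| Shift in all 50 set genes | Other true DEGs | Median set genes passing | GSEA, full list | GSEA, DEGs only | Over-representation |
|---|---|---|---|---|---|
| none | none | 0 / 0 | 3% / 3% | 0% / 0% | 0% / 0% |
| 0.5 SD | none | 0 / 0 | 100% / 100% | 0% / 0% (never runnable) | 0% / 0% |
| 0.5 SD | 500, mixed directions | 0 / 0 | 100% / 100% | 0% / 0% | 0% / 0% |
| 1 SD | 500, mixed directions | 3 / 5 | 100% / 100% | 11% / 22% | 7% / 16% |
| 1 SD | 500, same direction | 3 / 5 | 100% / 100% | 9% / 8% | 6% / 19% |
| 2 SD | 500, same direction | 27 / 32 | 100% / 100% | 8% / 4% | 100% / 100% |
| 2 SD | 500, mixed directions | 27 / 31.5 | 100% / 100% | 100% / 100% | 100% / 100% |

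The same-direction 2 SD row shows the mechanism. In the 5:10 split the median list has 311.5 DEGs, 27 of them in the set. That is 27/50 = 54% of the set, against (311.5 − 27)/4,950 = 5.7% of the other genes. The pathway is strongly enriched, yet GSEA on the DEGs detects it at about the nominal 5% rate.

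**Correlated genes.** A second set of runs used a 100-gene pathway with correlation 0.1, gene permutation on the DEGs and patient-label permutation on the full list.

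- All pathway genes shifted by 1 SD: 0% on DEGs against 98% on the full list with 5 responders, and 0% against 94% with 3.
- 40% of pathway genes and 5% of others strongly shifted in the same direction: 13% against 99.5%.
- No effect: the full list rejected in 3.5% of runs with patient labels, but in 39.5% with gene labels.

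This set changes list and permutation unit together, so it supports the direction of the loss rather than its exact size. It also shows that the table's full-list figures, from gene permutation on independent genes, should not be read as power in real, correlated data.

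**The case against.** The strongest reply is that IPA stands in the same sentence. Where a pathway holds many DEGs, over-representation against all tested genes found it in 100% of runs, so the study would usually still report it. That stands for strong effects. It does not cover the modest case: at 1 SD, over-representation found the pathway in 6-19% of runs in the table and 3-10% in runs with a 100-gene pathway.

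Second, the contrast is not stated. The sequencing paragraph is headed as a comparison before and after treatment, while its analysis sentence speaks only of comparison between patients. With a paired before/after contrast in 15 patients and a shift of 1 SD of the difference (assumed), the median was 27 DEGs rather than none, and over-representation found the pathway in 100% of runs. So a reader might infer that an empty DEG list is likely, but the documents do not establish that.

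Third, the sentence may simply be loosely drafted, with full-list GSEA intended. That is possible, but nothing elsewhere says so.

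Fourth, a reader might infer a permanent loss of information. That does not follow: DESeq2 tests every gene, so the full ranking can be rerun later. What would be lost is having fixed the method before seeing the results.

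Finally, this is one part of an exploratory aim, and Section 9.1 also plans microRNA, proteomic and metabolomic work. That limits the importance but does not make the rule right.

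**Conclusion.** The point holds on the plain text: GSEA as specified has the wrong input for its stated purpose. It can miss pathways linked to response, and it cannot run when no gene passes the cut-off. The clearest loss is for coordinated modest shifts with few DEGs, where detection fell from 100% to between 0% and 22% under the table's assumptions and IPA-type testing gave little cover.

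Two stronger readings are tempting. One is that such pathways will be missed. The table's last row contradicts this: with a strong pathway and other DEGs in mixed directions, both lists gave 100%. The other is a general loss of more than 80 percentage points. That appears only in the scenarios with few DEGs or same-direction DEGs, and it rests on an assumed group contrast, assumed effect sizes and t-tests in place of DESeq2.

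Nor does the full list by itself test whether a pathway is unrelated to response. With gene permutation it tests whether set genes rank no differently from all others; the stricter null needs permutation of patient labels. The consequence is confined to objective 2.3.1.

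**What to change.** In Section 9.1, replace the sentence with: 'The DEG list (FDR-corrected p < 0.05) will go to IPA, with all tested genes as the reference set. GSEA will be run on all tested genes, ranked by the signed DESeq2 statistic, without a significance filter.'

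Add the contrast and the permutation unit. Preferably permute patient labels for a group comparison, or before/after labels within each patient for a paired one, and refit the ranking each time. Gene permutation inflates false positives when genes are correlated. Where too few patients are available per group for useful p-values, report enrichment scores descriptively.

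The change needs no extra samples or assays, and DESeq2 already yields the full ranking. The costs are the computation for refitting and coarse p-values: with 2 responders among 15 there are only (15 × 14)/2 = 105 labelings, so the smallest p-value is 1/105, about 0.01.

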**PD-L1 Testing**

To ensure comparability of data across all studies of pembrolizumab and to gain real world experience on the performance of this assay, it is strongly encouraged that all studies that include PD-L1 testing utilize the Dako 22C3 assay.

**Estimate of volume of blood to be collected for research purposes**

The total volume of blood that will be drawn from each subject in this study is as follows:

